of treatment. Patients will be given continuous administration until disease progression as assessed by the investigator as per RECIST 1.1 or withdrawal from study or discontinuation criteria are met. As long as the investigator determines that the patient can continue to benefit from treatment, the patient may continue to receive treatment even if the patient has achieved disease progression defined by RECIST 1.1, and it is recommended to make a blinded judgment based on tumor response. According to current clinical practice, it is allowed to judge after unblinding if it is difficult to judge whether continuation of treatment is beneficial in a blinded manner; the treatment cannot be resumed once it is judged that there is no clinical benefit and the treatment is terminated. If additional treatment is provided, the baseline and follow-up schedules will not be affected by the additional treatment course.

● **Follow-up Period**

Subjects who discontinue treatment due to meeting the withdrawal or discontinuation criteria will complete the discontinuation follow-up; a 28-day safety follow-up will be completed after treatment discontinuation, followed by a survival follow-up every 6 weeks as per the study plan. Subjects who have no progress at the time of treatment discontinuation will continue to be followed up every 6 weeks (C1 to C21) or every 12 weeks (C23 and thereafter) until disease progression as assessed by the investigator as per RECIST 1.1, even if the patient has received other anti-tumor therapies; and then a survival follow-up will be performed every 6 weeks as per the study plan.

● **Open-label HS-10296 Crossover Treatment**

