7.11 Withdrawal Procedure

- 1) Recording the reasons: in any case, the investigator should collect the information of subjects as far as possible when subjects withdraw from the trial. The investigator should ask and record the reasons for withdrawal from the study of the subject, and retrieve the investigational product at the same time.
- 2) Discontinuation follow-up and safety follow-up: the discontinuation follow-up will be completed at the time of treatment discontinuation; thereafter, a 28-day safety follow-up will be performed to record AEs, SAEs, and concomitant medications. If there are abnormal and clinically significant changes, the abnormal condition should be followed up until recovery (to baseline, normal laboratory values, or abnormal values judged as clinically insignificant by the investigator) or stabilization.
- 3) Subsequent treatment: once the study treatment is discontinued, patients will receive further treatment according to the local standard of care. A patient may continue receiving the study treatment if the patient can continue to obtain clinical benefit from treatment as judged by the investigator, even if the patient has achieved disease progression defined by RECIST 1.1. Patients in the gefitinib treatment group who have disease progression and are eligible assessed by the study procedures may receive the open-label HS-10296 crossover treatment.
- 4) Progression follow-up: any patient who discontinues treatment for reasons other than

objective disease progression should have a scheduled follow-up for progression until disease progression as assessed by the investigator per RECIST 1.1, unless the patient withdraws informed consent.

5) Survival follow-up: if a subject withdraws consent to participate in study treatment and assessment, they should be further asked whether to continue survival follow-up via telephone. If a subject is unwilling to have the survival follow-up, the condition should be recorded in the eCRF. In such cases, no further evaluations should be performed and no further data should be collected. The Sponsor may retain and continue to use all data prior to withdrawal of informed consent by the subject. The screening and randomization numbers for subjects who withdraw consent cannot be reused.

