9.1.3.3 Progression Follow-up

Progression follow-up refers to the visit procedures to be completed by subjects who discontinue treatment for reasons other than disease progression. RECIST 1.1 assessments will be performed every 6 weeks (C1 to C21) or every 12 weeks (C23 and thereafter) (relative to the date of randomization). Patients who continue treatment after progression due to possible clinical benefit will continue to undergo tumor assessments. It includes the following items:

Progression follow-up for subjects who discontinue treatment for reasons other than disease progression:

- Response evaluations in solid tumors will be performed every 6 weeks (C1 to C21) or every 12 weeks (C23 and thereafter) until disease progression as assessed by the investigator per RECIST 1.1
- ECOG PS score will be performed every 6 weeks (C1 to C21) or every 12 weeks (C23 and thereafter) until disease progression as assessed by the investigator per RECIST 1.1
- Record concomitant medications: only subsequent anti-tumor therapy will be recorded in detail until disease progression
- If a subject has disease progression before the completion of the 28-day safety follow-up, the safety follow-up should be continued until 28 days after discontinuation of treatment

Progression follow-up for subjects who continue study treatment (donated drug) after disease progression:

- It is recommended to perform tumor assessments per RECIST 1.1 every 6 weeks (C1 to C21) or every 12 weeks (C23 and thereafter) until progression after the administration of donated drug as judged by the investigator or discontinuation of treatment before progression (safety reasons or investigator's judgment or subject's decision)
- ECOG PS score will be performed every 6 weeks (C1 to C21) or every 12 weeks (C23 and thereafter) until further progression as judged by the investigator or discontinuation of treatment before progression (safety reasons or investigator's judgment or subject's decision)
- Record concomitant medications: all concomitant medications (including anti-tumor therapy) will be recorded until 28 days after discontinuation of treatment, and only anti-tumor therapy will be collected thereafter
- Record adverse events: for subjects who continue to receive study treatment after progression, AEs and SAEs will be continued collecting until 28 days after discontinuation of treatment, and only AEs with no outcome and study drug-related SAEs will be collected thereafter

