10.2 Efficacy Evaluation

10.2.1 Response Evaluation in Solid Tumors as per RECIST 1.1

RECIST 1.1 will be used to assess each subject's response to anti-tumor therapy and to calculate PFS, ORR, DoR, DCR, and DepOR at the time of tumor assessments performed by the investigator. The standard definitions for measurable lesions, non-measurable lesions, TLs,

NTLs, complete response (CR), partial response (PR), stable disease (SD), and disease progression (PD), etc. specified by RECIST 1.1 are provided in [Appendix D](#). The analysis of the primary endpoint in this study will be based on the investigator's assessment of tumor response per RECIST 1.1, and the management of subjects by the investigator will only be performed based on the results of this assessment.

Baseline CT or MRI assessments of chest, abdomen, and brain tissue must be performed within 28 days prior to the start of study treatment (regardless of the time of signing the ICF), and it should be performed as close as possible to the start of study treatment. The investigator should perform additional imaging examinations based on the signs and/or symptoms of each subject. The same method as the baseline assessment (CT/MRI) should be used at each subsequent follow-up assessment. Brain metastases will be assessed as non-target lesions. If brain lesions are found at screening, a brain tumor assessment should be performed at each subsequent follow-up; for patients without brain metastases at baseline, brain metastasis assessments are not necessary at subsequent follow-up, whichever is necessary assessed by the investigator.

During the randomized treatment period, tumor response will be assessed every 6 weeks (\pm 1 week; C1 to C21) or every 12 weeks (\pm 1 week; C23 and thereafter) after randomization until disease progression as assessed by the investigator per RECIST 1.1. Tumor assessments should be performed as per the study plan whenever possible. If the assessment exceeds the scheduled timeframe (\pm 1 week) and the subject does not have disease progression, every effort should be made to perform subsequent assessments at the previously scheduled visit times while continuing study treatment. If a tumor is suspected at any other site, appropriate imaging examinations should also be performed at the suspected site.

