10.2.2 Central Review

All imaging data collected during the study, including tests performed during unscheduled visits, should be assessed with an independent central review (ICR) by a qualified Independent Review Committee (IRC) in accordance with the Imaging Independent Review Charter. The results of this independent assessment by the IRC will not be returned to the investigator.

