Appendix B Study Plan

• Study Plan for Randomized Treatment													
Visit ^a	Screening Period	Treatment Period								Study Discontinuation Follow-up	Follow-up Period		
		1	2	3	4	5	6	7-9	10+		28-day follow-up ^b	Progression Follow-up Every 6/12 weeks	Survival Follow-up Every 6 weeks
Treatment cycle ^c /day		C1 D1	C1 D8	C1 D15	C2 D1	C3 D1	C4-C6 D1	D1 of C7 and Every 6/12 weeks thereafter		NA	NA	NA	NA
Day	-28	1	8	15	22	43	64-106	127+		NA	NA	NA	NA
Window period (days)	NA	0	±2	±2	±2	±7	±7	±7		+7	NA	±7	±7
Informed consent	×												
Demographic and baseline characteristics	×												
Medical/surgical history	×												
Inclusion/exclusion criteria	×												
EGFR mutation test	×												
Physical examination (including body weight) ^d	×	×			×	×	×	×	×				
Body Height	×												
ECOG PS score	×	×			×	×	×	×	×			×	
Pregnancy test	×												
Ophthalmological Examination	×	Ophthalmic examination performed within 48 hours as clinically indicated											
Vital signs ^d	×	×	×	×	×	×	×	×	×				
Clinical chemistry/hematology/urinalysis ^d	×	×	×	×	×	×	×	×	×				

• Study Plan for Randomized Treatment												
Visit ^a	Screening Period	Treatment Period							Study Discontinuation Follow-up	Follow-up Period		
		1	2	3	4	5	6	7-9		28-day follow-up ^b	Progression Follow-up Every 6/12 weeks	Survival Follow-up Every 6 weeks
Treatment cycle ^c /day		C1 D1	C1 D8	C1 D15	C2 D1	C3 D1	C4-C6 D1	D1 of C7 and Every 6/12 weeks thereafter	NA	NA	NA	NA
Day	-28	1	8	15	22	43	64-106	127+	NA	NA	NA	NA
Window period (days)	NA	0	±2	±2	±2	±7	±7	±7	+7	NA	±7	±7
Electrocardiogram ^e	×	×	×	×	×	×	×	×	×			
Echocardiography (LVEF)	×	Every 12 weeks from the first dose and as clinically indicated						×				
Collection of tumor and/or blood samples at disease progression during the randomized treatment phase (optional)									×			
Tumor assessment (RECIST v1.1) ^f	×	Every 6 weeks ± 7 days (first 15 months; C1 to C21)/every 12 weeks (after Month 15; C23 and thereafter) after randomization										
Drug dispensing		×			×	×	×	×				
Drug intake		Dosing everyday										
Concomitant medications	↔									×	Occurring prior to completion of 28-day follow-up	
Adverse Event	↔											
Anti-tumor therapy	×									×	×	
Subsequent response/progression data ^g											×	
Survival status ^h											×	

• Study Plan for Randomized Treatment												
Visit ^a	Screening Period	Treatment Period							Study Discontinuation Follow-up	Follow-up Period		

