		1	2	3	4	5	6	7-9		28-day follow-up ^b	Progression Follow-up Every 6/12 weeks	Survival Follow-up Every 6 weeks
Treatment cycle ^{c/day}		C1 D1	C1 D8	C1 D15	C2 D1	C3 D1	C4-C6 D1	D1 of C7 and Every 6/12 weeks thereafter	NA	NA	NA	NA
Day	-28	1	8	15	22	43	64-106	127+	NA	NA	NA	NA
Window period (days)	NA	0	±2	±2	±2	±7	±7	±7	+7	NA	±7	±7
Comments	
a. Subjects will be followed every 3 weeks (1 cycle) from Cycles 1 to 6; every 6 weeks (2 cycles) from Cycle 7 onwards; and two additional visits will be added on C1D8 and C1D15.
 
b. Subjects should be followed up by telephone 28 days (± 7 days) after discontinuation of study drug.
 
c. One cycle is defined as 21 days of continuous treatment.
 
d. These assessments at baseline should be completed prior to dosing on the visit day. If screening tests are completed within 7 days prior to the first dose of investigational product, they will not be required to perform on C1D1.
 
e. ECGs may be performed in the event of any cardiac-related AE.
 
f. Baseline tests should be performed within 28 days prior to the first dose. Assessments will be performed every 6 weeks after the start of treatment until disease progression as determined by centralized assessment per RECIST 1.1 criteria, even if the subject discontinues treatment prior to progression or has received other anti-tumor therapies. Tumor assessment data will be obtained from CT or MRI (contrast-enhanced CT or MRI is recommended to be preferred).
 
g. Tumor response results assessed by the investigator will be collected.
 
h. Subjects should be contacted to determine their survival status after the data cutoff date as determined by OS analysis.
											

• Study Plan for HS-10296 Crossover Treatment												
Visit ^a	HS-10296 Pre-crossover Visit	Treatment Period							Study Discontinuation Follow-up	Follow-up Period		
		2	3	4	5	6	7-9	10+		28-Day Follow-up	Progression Follow-up Every 6 weeks	Survival Follow-up Every 6 weeks
Treatment cycle ^b	C0	C1	C1	C1	C2	C3	C4-C6	Every 6 weeks from C7 onwards	NA	NA	NA	NA
Day	-28	D1	D8	D15	D22	D43	D64-106	D127	NA	NA	NA	NA
Window period (days)	NA	0	±2	±2	±2	±7	±7	±7	+7	NA	±7	±7
Informed consent	×											
Collection of tumor/blood samples after disease progression during the randomized treatment phase	×											
T790M mutation test	×											
Tumor assessment	×	The assessment is recommended to perform every 6 weeks ± 7 days per RECIST 1.1									×	

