4.1 Assessment Schedule

CT examination of chest and abdomen (including liver and adrenal glands) will be used to assess tumor burden at baseline and during follow-up visits. CT examination with contrast administered intravenously is the preferred method. MRI should be used when CT is not feasible or is medically contraindicated.

Baseline tumor assessments should include all regions where the disease under evaluation is known to metastasize, should include additional assessments of areas that may be involved based on the signs and symptoms of individual patients, and should be performed no more than 28 days prior to the start of study treatment. Follow-up assessments should be performed every 6 weeks (\pm 7 days) from the start of treatment until discontinuation of study treatment or withdrawal of consent. If new lesions are suspected elsewhere, imaging should be performed during follow-up.

If an unscheduled assessment has been performed and there is no disease progression, every effort should be made to perform subsequent assessments on the patient at his/her scheduled visits. The schedule will be followed in order to minimize any unintentional deviations caused by the frequency of follow-up assessments of some patients differing from those of others.

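### Appendix B note f and Appendix D 4.1 give tumor assessment rules that contradict the protocol body and the SAP

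*Protocol*

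**What the plan says.** **Governing rule.** Protocol 6.1 says that patients who stop treatment without progression "will continue to be followed up every 6 weeks (C1 to C21) or every 12 weeks (C23 and thereafter) until disease progression as assessed". The assessor there is the investigator, and later anti-tumor therapy does not end the scans. Protocol 9.1.3.3 schedules these assessments "every 6 weeks (C1 to C21) or every 12 weeks (C23 and thereafter) (relative to the date of randomization"), and SAP 1.2.2.3.3 agrees. Protocol 10.2.1 gives the same 6- and 12-week intervals "after randomization until disease progression as assessed by the investigator per RECIST 1.1". Protocol 7.11 says that a patient whose ground for stopping is anything but "objective disease progression should have a scheduled follow-up for progression until disease progression as assessed by the investigator per RECIST 1.1". Protocol 12.1.3 also requires imaging to continue to RECIST progression after treatment stops.

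**Appendix B.** The tumor assessment row has 6-week scans for the first 15 months and then "every 12 weeks (after Month 15; C23 and thereafter) after randomization". Note f, attached to that row, says "Assessments will be performed every 6 weeks after the start of treatment until disease progression as determined by centralized assessment per RECIST 1.1 criteria". The same sentence goes on to say that assessments continue after treatment discontinuation or other therapy.

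**Appendix D 4.1.** Follow-up scans are every 6 weeks "from the start of treatment until discontinuation of study treatment or withdrawal of consent".

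**Central review.** Protocol 10.2.2 states: "The results of this independent assessment by the IRC will not be returned to the investigator".

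**The concern.** PFS by investigator assessment is the primary endpoint, and a scan not done at its scheduled time cannot be recovered. Site staff consult these two appendices: Protocol 9.1 names Appendix B as the overall follow-up schedule, and 10.2.1 refers to Appendix D for RECIST. Note f gives an interval that its own table row contradicts and a stopping point the site has no information to apply. Appendix D 4.1 ends imaging at treatment discontinuation, so progressions after that date would not be observed.

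SAP Table 4.2-1 (secondary censoring rules, output 14.2.4) does not censor at treatment termination, so it relies on those progressions. The analysis would be weakened but not emptied, because Table 4.2-1 also drops the censoring after two missed visits in Table 4.1-2.

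The effect on the primary analysis depends on the termination row of Table 4.1-2, which is ambiguous. If it censors every stop before imaging progression, no primary events are lost. If it censors only stops for clinical, non-imaging progression, other off-treatment progressions are lost from the primary analysis too.

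**Working it through.** **Comparison of the texts**

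| Source | Interval | Stopping point | Scans continue off treatment? |
|---|---|---|---|
| 6.1, 9.1.3.3, SAP 1.2.2.3.3 | 6 weeks, then 12 from C23 | Investigator progression | Yes |
| 10.2.1 | 6 weeks, then 12 from C23 | Investigator progression | Not addressed |
| 7.11 | Not given | Investigator progression | Yes |
| 12.1.3 | Not given | RECIST progression | Yes |
| Appendix B row | 6 weeks, then 12 from C23 | Not given | Not given |
| Appendix B note f | 6 weeks throughout | Central progression | Yes |
| Appendix D 4.1 | 6 weeks throughout | End of treatment or consent withdrawal | No |
| Appendix D 4.5 (stop for symptomatic deterioration) | Per protocol | Objective progression | Yes |

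Counting from start of treatment or from randomization is not a real conflict, because SAP 1.2.4 puts both on the same day.

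**Plan's own figure.** Inputs from Protocol 5.3: HR 0.67 (medians 10 and 15 months), 1:1 allocation, 8 months' enrollment, 23 months in total, two-sided alpha 0.05, 262 events, about 410 patients. Schoenfeld power is Φ(½√D·|ln HR| − 1.96). With D = 262 and HR 0.67: ½ × 16.19 × 0.4005 − 1.96 = 1.28, or 90.0%. The plan's figure is reproduced.

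**Expected events.** Exponential PFS, 205 per arm, uniform accrual. For a hazard k per month, the probability of leaving follow-up by that hazard before cutoff is A(k) = 1 − (e^(−15k) − e^(−23k))/(8k).
- Gefitinib, λ = ln 2/10: 205 × A(λ) = 149.4
- HS-10296, λ = ln 2/15: 205 × A(λ) = 119.3
- Total: 268.7

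**Events lost under Appendix D 4.1.** Let μ be a constant monthly hazard of stopping before progression, equal in both arms. Per arm, the number stopping is 205·μ/(λ+μ)·A(λ+μ), and the events still seen on treatment are 205·λ/(λ+μ)·A(λ+μ). μ is solved so that 5, 10 or 15% of the 410 stop (assumed; the documents give no rate). All sites are assumed to follow 4.1. Power is at HR 2/3 (|ln HR| = 0.4055); with 268.7 events it is ½ × 16.39 × 0.4055 − 1.96 = 1.36, or 91.4%.

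| Stop before progression | μ | Patients | Events lost | Share of 268.7 | Events left | Power | Lost if hazard doubles after stopping |
|---|---|---|---|---|---|---|---|
| 5% | 0.00448 | 20.5 | 9.1 | 3% | 259.5 | 90.4% | 13.5 |
| 10% | 0.00930 | 41 | 18.5 | 7% | 250.2 | 89.4% | 27.1 |
| 15% | 0.01451 | 61.5 | 28.0 | 10% | 240.7 | 88.2% | 41.0 |

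Within each scenario the loss is an upper bound, because deaths are still recorded in survival follow-up.

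**Hazard ratio.** Simulation of an analysis that counts off-treatment events: 1,500 trials, scans on days 43 to 463 every 42 days and then every 84 days. Where off-treatment scans are missing, patients who stop are censored at their last scan before stopping.

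| % stopping, gefitinib / HS-10296 | Hazard multiplier after stopping | HR with off-treatment scans | HR without |
|---|---|---|---|
| 5 / 5 | 1 | 0.679 | 0.679 |
| 10 / 10 | 1 | 0.679 | 0.677 |
| 15 / 15 | 1 | 0.678 | 0.676 |
| 5 / 15 | 1 | 0.677 | 0.681 |
| 15 / 5 | 1 | 0.678 | 0.672 |
| 10 / 10 | 2 | 0.676 | 0.676 |
| 5 / 15 | 2 | 0.707 | 0.680 |
| 15 / 5 | 2 | 0.644 | 0.672 |

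**Interval conflict alone.** C23D1 is day 1 + 21 × 22 = 463. By month 23 (day 700), 6-weekly scanning throughout gives 16 post-baseline scans and the governing rule gives 13. About 34 of 269 expected events fall after month 15. With 0/50/100% of sites scanning 6-weekly after C23 (3,000 paired trials, 40 sites assumed), HR is 0.678/0.677/0.676 and power 90.8/91.1/91.4%.

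**The case against.** The strongest reply is that the design itself is clear and this is leftover appendix wording. Note f supports the off-treatment rule in the rest of its sentence. Its interval error is immaterial, and because sites never receive central results they would fall back on investigator progression anyway. Appendix D is a RECIST guide rather than the visit schedule, and its section 4.5 defers to the protocol. Appendix B has a progression follow-up column at 6/12 weeks. To lose scans, a site would have to overlook that column, note f, 6.1, 7.11, 9.1.3.3, 10.2.1, 12.1.3 and Appendix D 4.5. The figures assume that all sites do so, at stopping rates the documents do not give. The power figures describe an analysis that may be only a sensitivity analysis, while the plan's 90% is for the main comparison.

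Most of this stands as a limit on size. The real loss should be well below the all-sites figures, note f is not the source of any lost events, and the primary analysis may be untouched. It does not remove the defect. Appendix D 4.1 is current text that states a stopping point for PFS imaging, and following it as written loses data that 12.1.3 requires. Note f contradicts its own row and cannot be carried out as worded.

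**Conclusion.** The concern holds. Both appendix texts conflict with the governing rule, and Appendix D 4.1 is the consequential one. If all sites followed it and 5 to 15% of patients stopped before progression, 9 to 28 of 269 expected events would be lost (13 to 41 if the hazard doubles after stopping). With no change in hazard after stopping, power of an analysis counting those events would fall by about 1 to 3 points. Bias is negligible (HR shift at most 0.006) unless stopping differs by arm and is also followed by a higher hazard. With 15% against 5% stopping and a doubled hazard, the HR moves by about 0.03, in either direction depending on which arm stops more. That would be informative censoring, which a larger event count would not repair.

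Stopping rates, the post-stop hazard and full site adherence to 4.1 are all assumptions. Whether the primary analysis is affected depends on how the Table 4.1-2 termination row is read. The interval conflict has no material effect, and alpha, event target and sample size do not change. This should be corrected, but it does not invalidate the design.

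**What to change.** Reword Appendix B note f and Appendix D 4.1 to the governing rule: scans every 6 weeks to C21 and every 12 weeks from C23, timed from randomization, until investigator-assessed RECIST 1.1 progression, regardless of treatment discontinuation or new anti-tumor therapy. In the same amendment, remove the similar leftover in Protocol 10.1.1, which makes crossover consent follow central confirmation of progression, although 6.1 and 9.2.1.1 rest it on the investigator's assessment.

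The cost is one footnote and one appendix paragraph, plus the 10.1.1 sentence, handled through the usual amendment and ethics committee process. Sample size, visits and analyses do not change.
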